#### 7.5.3. Laboratory Test Results

All Hematology and Chemistry laboratory data will be summarized by change and % change from Baseline to each post baseline scheduled visit. For Urinalysis change and % change will only be done for pH.

Analysis of hematology and chemistry abnormalities will include a summary of abnormalities between baseline and worst post baseline visits based on criteria indicated on eCRF (Abnormal CS, Abnormal NCS, Normal, Not Done).

In addition a shift Table will display changes in status from baseline to worst post-treatment value will be summarized. The order of determining worst will be abnormal clinically significant > abnormal not clinically significant > not done.

A shift Table will summarize Serology Tests between Non-Reactive and Reactive.

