7.2.3. Laboratory tests and serology

The tests to be performed in the study are described below. In visits in which there is the administration of the product, samples for laboratory tests should be collected before the beginning and after 06h 00min of the end of product administration.

Table 03. Laboratory tests to be performed on V-3 and in all post-cycle follow-up visits (V3, V7, V11)

Category	Test	Normality values	
Hematological Analysis	Hemogram (erytrogram, leukogram and platelet count)		
	Serum sodium		
Biochemical Analysis	Serum potassium		
	Amylase		
	Total cholesterol and fractions (LDL, HDL and VLDL)		
	Triglycerides	According to the reference	
	Coagulogram (RNI, TAP and TTPA)	values established by the laboratory.	
	Alkaline phosphatase		
	Glycated hemoglobin (HbA1c)		
	Urea		
	Uric acid		
	TGO		
	TGP		
	Gamma-GT		

Category	Test	Normality values
	Total bilirubin and fractions	
	Serum creatinine	
	CK	
	CKmB	
Urological Analysis	Urine summary (urine I)	
Other	β-hCG urinary (women-only)	

Table 04. Serological tests to be performed in the study at visits V-3 and V11.

	HIV (1 + 2) (Anti-HIV-1.2)	
	HTLV I and II	
Serological Analysis	HBV (HbsAg and Anti-HBc)	Negative
	HCV (anti-HCV-Ab)	
	FTA-ABS (syphilis)	

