### 3. Study Design

[figure not shown]
This study is a prospective, phase II, single-center, randomized, placebo controlled, triple-blind study evaluating two test doses vs placebo in 35 participants randomized 2:2:1 into the following treatment groups:

G1: (n = 14 participants) - Lower dose: dose of  $1 \times 10^6$  cells/by weight range per administration.

G2: (n = 14 participants) - Higher dose: dose of  $2x10^6$  cells/by weight range per administration.

G3: (n = 7 participants) - Placebo: constituted by the vehicle of the investigational product.

After a 90 days screening period, participants will be included in the study and will begin treatment and follow-up phase that will last 330 days. The total period of participation in the study will be up to 420 days from the period of uniformization of the study; that is, about 14 months approximately (See figure below). Note: Ciclo below means Cycle.

Above visits take place as indicated below (for additional details on windows around visits, see schedule of assessments)

- Visit -3 inclusion (V-3): -30 to -1 days before V-2;
- Visit -2 (V-2): up to 30 + 7 days after V-3
- Visit -1 (V-1): up to 30 + 7 days after V-2
- Visit 0 (V0): first administration of cycle 1; up to 30 days after V-1
- Visit 1 (V1): second administration of cycle 1 (30 days after Visit 0)
- Visit 2 (V2): third administration of cycle 1 (60 days after Visit 0)
- Visit 3 (V3): follow-up visit (90 days after Visit 0)
- Visit 4 (V4): first administration of cycle 2 (120 days after Visit 0)
- Visit 5 (V5): second administration of cycle 2 (150 days after Visit 0)

F-SA-06-01, Version 5.0/30 Dec 2021, SOPs Link: SOP-SA-06

- Visit 6 (V6): third administration of cycle 2 (180 days after Visit 0)
- Visit 7 (V7): follow-up visit (210 days after Visit 0)
- Visit 8 (V8): first administration of cycle 3 (240 days after Visit 0)
- Visit 9 (V9): second administration of cycle 3 (270 days after Visit 0)
- Visit 10 (V10): third administration of cycle 3 (300 days after Visit 0)
- Visit 11 (V11): follow-up visit/final visit (330 days after Visit 0)

After the 11th Visit, participants will enter an extension protocol.

Subjects will be randomized and treatment initiated at V0.

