#### 5. Statistical Hypothesis

This study is a Phase II study to determine efficacy and safety of Cellavita HD. Hypothesis tests for efficacy will be conducted as described below. No hypothesis testing will be performed on any safety data.

All hypothesis tests will be at the two-sided 5% significance level (Two-sided Type I error of 0.05)

H0: There is no difference in rate of change (slope) per year from Baseline through V11 in TMS between the two pooled active treatment groups and the placebo group

Ha: There is a difference in rate of change (slope) per year from Baseline through V11 in TMS between the two pooled active treatment groups and the placebo group

The following statistical tests will be performed:

- 1. Between the two active pooled treatment groups and placebo (primary)
  Participants receiving either 1 million or 2 million cells per kg (Treated) vs. Placebo
- Between each of the two active treatment groups individually and placebo (to determine efficacy of each treatment group compared to placebo)
   Participants receiving 1 million cells per kg (Treated) vs. Placebo
   And Participants receiving 2 million cells per kg (Treated) vs. Placebo
- 3. Between the two active treatment groups to assess similarity between the two treatment groups.

F-SA-06-01, Version 5.0/30 Dec 2021, SOPs Link: SOP-SA-06

Participants receiving 1 million vs. 2 million cells per kg.

The same tests performed for TMS will also be performed for other continuous endpoints.

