Early termination visits will be allocated to the nearest scheduled visit where data was to be collected but is not recorded.

All analyses of changes, % changes, etc. will be by scheduled visits.

For analyses of abnormalities, data from both scheduled visits and unscheduled visits will be included.

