#### 7.2. Data Handling

#### 7.2.1. Premature Withdrawal and Missing Data

The following imputation rules will be used for prior and concomitant medications.

Partial or missing start date for concomitant medication

- 1. Incomplete or partial start date will not be imputed if end date of concomitant medication is on or before treatment start date.
- 2. Incomplete or missing start date will be imputed as mentioned below if end date of concomitant medication falls after treatment start date (or if medication is ongoing at EoS for treated participants).

Handling of partial/missing dates for Medication

Partial/Missing Start Date

- 1. Missing day Impute the 1st of the month unless month and year is same as month and year of first dose of study drug then impute first dose date.
- 2. Missing day and month impute 1st January unless year is the same as first dose date then impute first dose date.

Partial/Missing End Date

- 1. Missing day Impute the last day of the month unless month and year is same as month and year of last dose of study drug then impute last dose date.
- 2. Missing day and month impute 31st December unless year is the same as last dose date then impute last dose date.

No other imputation of missing data for safety assessments will be made. Wherever possible missing data will be summarized as a category.

No imputation for missing data will be made as the mixed model repeated measures incorporates missing data.

Additional analyses may be conducted for FDA, EMA or other regulatory agencies if required and deemed appropriate under assumptions of MAR and MNAR using MI.

The eCRF did not allow entry of partial AE dates so no imputation of start or stop dates will be performed.

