#### 7.5.4. 12 lead electrocardiogram

Analysis of ECG abnormalities will include a summary of abnormalities between baseline and at worst post baseline visits based on criteria indicated on eCRF (Abnormal CS, Abnormal NCS, Normal, Not Done).

In addition a shift Table will display changes in status from baseline to worst post-treatment value will be summarized. The order of determining worst will be abnormal clinically significant> abnormal not clinically significant> normal.

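### The laboratory shift-table rule in SAP 7.5.3 ranks Not Done but leaves Normal unranked, so the worst category is undefined for all-normal records and for normal records with a missed draw

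*SAP*

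**What the plan says.** SAP 7.5.3 summarises haematology and chemistry abnormalities at baseline and at the worst post-baseline visit, "based on criteria indicated on eCRF (Abnormal CS, Abnormal NCS, Normal, Not Done". That gives four statuses. It then adds a shift table from baseline to the worst post-treatment value and defines worst in one sentence: "The order of determining worst will be abnormal clinically significant > abnormal not clinically significant > not done". Only three of the four statuses are ranked, and Normal is the one left out.

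SAP 7.5.4 plans the same pair of displays for the ECG with the same four statuses, but its rule reads: "The order of determining worst will be abnormal clinically significant> abnormal not clinically significant> normal". Here Not Done is the status without a rank.

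Three other statements bear on the point:

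- The heading of Table 03 in Protocol 7.2.3 sets the schedule: "Laboratory tests to be performed on V-3 and in all post-cycle follow-up visits (V3, V7, V11". That is one baseline draw and three post-baseline draws.
- SAP 7.2.1 says of safety data: "Wherever possible missing data will be summarized as a category".
- SAP 7.1 says: "For analyses of abnormalities, data from both scheduled visits and unscheduled visits will be included".

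Neither document says how Normal compares with Not Done for a laboratory test, or how a participant who has both is to be classed.

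**The concern.** A worst-value rule has to return one category for every participant and every test. This one does not. For most tests the expected course is normal throughout, and that course has no ranked value. Where normal results sit beside a draw recorded as Not Done, the only ranked status present is Not Done, so a program that follows the sentence would return it. A missing draw would then displace results that were actually observed, although a missing value is not a worse finding than a normal one.

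What is at stake is the normal post-treatment column of the laboratory shift table, and in particular the normal-to-normal cell. SAP 5 states: "No hypothesis testing will be performed on any safety data". The laboratory safety message therefore rests on descriptive displays, and this table is one of them. If arms differed in missed draws, their normal counts could differ for that reason alone. The laboratory and ECG tables would also treat the same data pattern differently within one report.

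**Working it through.** The plan states no figure on this point, so there is nothing to reproduce. The check has two parts.

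**1. What the rule returns.** Take one participant and one test, with draws at V3, V7 and V11 (Protocol 7.2.3, Table 03) and no abnormal result. Each draw is Normal or Not Done, which gives 2 × 2 × 2 = 8 patterns.

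| Pattern | Number of patterns | 7.5.3 taken literally | Not Done ranked above Normal | Normal ranked above Not Done |
|---|---|---|---|---|
| All three Normal | 1 | no ranked status | Normal | Normal |
| Mixed Normal and Not Done | 6 | Not Done, if the only ranked status present is taken | Not Done | Normal |
| All three Not Done | 1 | Not Done | Not Done | Not Done |

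With Not Done above Normal, 1 of 8 patterns is classed as Normal and 7 as Not Done. With Normal above Not Done, 7 are classed as Normal and 1 as Not Done. The 6 mixed patterns make the difference, and their class depends on a choice that the SAP does not state. If any draw is abnormal, CS or NCS ranks first under every reading, so the abnormal counts do not move.

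**2. How often a mixed pattern could arise.** The documents give no missed-draw rate. Assume that each of the three draws is missed independently with probability p, that a missed draw is recorded as Not Done, and that all other results are normal. A mixed pattern means at least one draw missed but not all three:

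mixed share = 1 − (1 − p)³ − p³

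| p (assumed) | At least one missed | All three missed | Mixed |
|---|---|---|---|
| 0.05 | 0.1426 | 0.0001 | 0.1425 (14.3%) |
| 0.10 | 0.2710 | 0.0010 | 0.2700 (27.0%) |
| 0.20 | 0.4880 | 0.0080 | 0.4800 (48.0%) |

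The all-missed share has to come out, because those participants have no post-baseline result and are correctly Not Done.

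SAP 3 describes a study "evaluating two test doses vs placebo in 35 participants randomized 2:2:1", that is 14, 14 and 7. If every participant in an arm were otherwise normal on the test, the mixed share at p = 0.10 would be 14 × 0.27 = 3.8 participants in each active arm and 7 × 0.27 = 1.9 on placebo. At p = 0.05 it would be 2.0 and 1.0; at p = 0.20, 6.7 and 3.4. Under these assumptions the counts are upper limits, since not every participant will be otherwise normal.

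**The case against.** The strongest reply is that this is a slip of the pen. SAP 7.5.3 names Normal among the statuses a few lines earlier, and SAP 7.5.4 repeats the sentence almost word for word with normal in the last place. If normal was meant, a programmer who read it that way would produce correct counts. That is plausible, and nothing shows that ranking missing data above normal was a deliberate choice. But tables are programmed from this sentence, and SAP 7.2.1 asks for missing data to be shown as a category, so a programmer could also take Not Done as intended. A slip here still needs correcting.

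A reader might infer that a participant with normal tests and one missed draw will be classed as Not Done, so that the normal-to-normal count is wrong. The documents do not say so. Normal is unranked, so the outcome is undefined. The misclassification also requires the missed draw to be entered as Not Done, and no section says that an absent visit creates such a record.

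A reader might also infer that missed draws are likely because SAP 7.4.1 says COVID-19 disturbed the visit schedule. Late visits would fit that remark equally well, and no rate is given. The three-draw model is also simplified: SAP 7.1 brings in unscheduled visits and allocates early-termination visits to the nearest scheduled visit that has no record.

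Finally, the shift table is not the main laboratory display. SAP 7.5.3 puts change and percentage change by scheduled visit first and introduces the shift table as an addition. SAP 7.1 lists all data from the case report form, and SAP 7.3.1 tabulates completion of each visit. Observed normal results therefore stay visible elsewhere. All of this stands, and it limits the point to a minor one. It does not supply the missing rank.

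**Conclusion.** The laboratory rule is defective as written. It ranks three of four statuses, gives no worst value to an all-normal course, leaves a mix of Normal and Not Done to the programmer, and differs from the ECG rule without a stated reason. Followed literally, it could understate the normal post-treatment counts in the laboratory shift table.

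The consequence is small and confined to the split between Normal and Not Done in one descriptive table. No abnormal finding is hidden and no inference changes. The percentages above show only how the mixed share grows with the miss rate; they rest on assumed rates, independence, three draws, and misses recorded as Not Done. They are not a forecast for this trial. The documents support neither the claim that the count is wrong nor the claim that many participants will be misclassified. They do show that the class is unspecified for 6 of the 8 patterns without an abnormal result, and that a seventh, all normal, has no rank.

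**What to change.** Change the order in SAP 7.5.3 to abnormal CS > abnormal NCS > normal, matching SAP 7.5.4. In both sections, add that Not Done is assigned only when the participant has no post-baseline result for that test. The addition is needed for the ECG as well, where a participant with no post-baseline tracing has no category at present. Showing the number of participants with a result at each visit would keep missed draws visible, in line with SAP 7.2.1.

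The cost is one sentence in each section and a line of table programming. There is no statistical downside: the CS and NCS counts are unchanged, and participants with no post-baseline result are still reported as such.

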#### 7.5.4. 12 lead electrocardiogram

Analysis of ECG abnormalities will include a summary of abnormalities between baseline and at worst post baseline visits based on criteria indicated on eCRF (Abnormal CS, Abnormal NCS, Normal, Not Done).

In addition a shift Table will display changes in status from baseline to worst post-treatment value will be summarized. The order of determining worst will be abnormal clinically significant> abnormal not clinically significant> normal.

#### 7.5.5. Vital Signs

Vital signs data will be summarized by change and % change from Baseline to each post baseline scheduled visit.

During visits when study drug was administered, Vital signs were performed Before drug administration, During drug administration and After drug administration and will be summarized as such.

Analysis of vital sign abnormalities will include a summary of CS and NCS abnormalities between baseline and worst post baseline visits visit.

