6.3. Dosage

In this study, two different doses of the investigational product will be evaluated ($1x10^6$ cells/by weight range and $2x10^6$ cells/weight range) compared to placebo. Therefore, each participant will receive according to randomization, one of the fractional doses of Cellavita-HD product in 0.9% saline or placebo.

Each participant will receive three cycles of three consecutive administrations (one every 30 days) with the drug according to randomization. The interval between cycles will be 30 days. The following table also summarizes the distribution of participants among the treatment groups, as well as the dosage and the route to be used.

Table 02. Possible treatment groups in the ADORE-DH study

Group	Dose	Dosage	Administration	Investigative Product	Way
G1	Lower dose	1x10 ⁶ cells/weight range	3 administrations (one every 30 days) per cycle	· Cellavita-HD	Intravenous
G2	Higher dose	2x10 ⁶ cells/weight range	3 administrations (one every 30 days) per cycle		
G3	Placebo	Investigational product vehicle	3 administrations (one every 30 days) per cycle	Placebo	Intravenous

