8.7.1.1.3. Analysis of the safety hypothesis

The safety assessment will be performed at the end of each cycle and will be verified through the incidence of reports that adverse events occurred during the study, in relation to causality with the treatment under study.

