9.5. Expected adverse events with cell therapy

Few adverse events have been reported after administration of mesenchymal stem cells in terms of immediate toxicity, infusion and late effects. Thus, as the number of patients on therapy with this type of cell is still relatively small, adverse events and safety related to it have not yet been fully elucidated. However, in some specific pathological cases, the use of mesenchymal stem cells

was related to the appearance of neoplasms (history of neoplasms) and worsening of arthritis (history of arthritis) (Wang, Qu & Zhao, 2012).

In order to gather information on adverse events related to mesenchymal stem cell therapies and to support their use in clinical studies, Lalu et al. (2012) conducted a meta-analysis in which no significant associations were verified between treatment with mesenchymal stem cells (of several lines) and the development of acute infusion toxicity, systemic complications, infections, neoplasms or deaths. However, the authors found that although there is a significant correlation between cell therapy and the onset of transient fever, it is possible to observe good tolerability and safety (Lalu et al., 2012).

Although the appearance of neoplasms is a risk to the use of cell therapies, the analysis performed by the authors did not find an association between both. The emergence of this correlation started from non-clinical studies that demonstrated neoplastic increase in animals treated with therapy, however, in current clinical studies the occurrence of neoplasia presented was low and present only in patients with a history of neoplasms (Lalu et al., 2012).

Thus, the authors concluded that despite the need for broader and more controlled clinical studies involving the use of mesenchymal stem cells for long periods, so far there is no evidence that this therapy represents a safety risk to humans (Lalu et al., 2012).

This way, due to the variety of theoretical risk factors involving this therapy, a thorough clinical evaluation should be performed, taking into account the risks and benefits that treatment may present for the patient. This assessment at the beginning and during follow-up of cell therapy can help determine the extent and focus of safety plans for such treatment (Herberts, Kwa & Hermsen, 2011; Wang, Qu & Zhao, 2012).

The table below summarizes the possible theoretical risk factors involving the use of cell therapy with mesenchymal stem cells of several lines.

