Table 05. Theoretical risk factors involved in mesenchymal stem cell therapy.

Table 05. Theoretical risk factors involved in mesenchymal stem cell therapy.	
Factors	Possible risks
Intrinsic	 Rejection of administered cells Susceptibility to opportunistic diseases Grafting cells in an unwanted location Unwanted biological effect (differentiation in vivo in unwanted cell types) Toxicity (infusion or systemic) (Symptoms: transient fever, bronchospasm and/or laryngospasm, chills, diarrhea, dyspnea, headache, facial edema, glottis and/or larynx, fever, hemoglobinuria, hypotension, nausea, itching, facial flushing, abnormal bleeding, sweating, tachycardia, dizziness, hives, and vomiting). DMSO toxicity (Symptoms: cough, flushing, rash, chest tightening and wheezing, nausea and vomiting, cardiovascular instability). Formation of neoplasms (malignant or benign)
Extrinsic	 Transmission of diseases Reactivation of latent viruses Unwanted immune response Cell contamination (with unwanted cells, culture media components or chemical compounds); Mixture of autologous patient material Cardiac, vascular, renal, neurological, pulmonary, hematological or hepatic dysfunctions Formation of neoplasms (malignant or benign)

Source: Circulation of Information for use of cellular therapy products – Revised November 2013. Helberts, Kwa & Hermsen, 2011; Lalu et al., 2012 - Adapted.

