#### 6. Analysis Populations (Datasets)

According to the principles of intent to treat (ITT) analysis as defined in ICH E9, all participants who have been randomized will be considered as part of the ITT population... Participants will be tabulated based on treatment group to which they are randomized.

The Safety Population will include all participants who received at least one dose of study medication. Participants will be tabulated based on treatment group they actually received.

A Per Protocol (PP) population will be defined as all participants who received all 9 infusions. Participants will be tabulated based on treatment group they actually received.

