#### 7. Statistical Methods

#### 7.1. General Statistical Consideration

All analysis (generation of Tables, Figures and Listings) will be performed using SAS 9.4 or newer.

All statistical Tables will summarize data by the following columns (or rows when summary Table is by treatment groups in rows) Low Dose, High Dose, Low & High Dose, Placebo, Total. If there are space limitations the Total column can be excluded. A footnote will clarify what Low and High Dose refer to.

All data collected on the eCRF will be included in the Listings. Some data will only be in Listings and no summary Tables or Figures will be created.

The eCRF collected participant initials and date of birth (The concatenation of these is variable SUBNUM in the dataset). For participant privacy this data will not be included in any Tables or Listings but will be retained in the analysis database. The Site ID and internal ID will be used to create a new unique Participant ID. In Listings this new Participant ID will be used as the unique identification of participants in this study.

Descriptive statistics for continuous data will include the mean, standard deviation, median, minimum, maximum, Q1, Q3.

Categorical data will be summarized by the frequency and percentages within each category. Unless otherwise specified the denominator for the %'s will be the number of participants randomized to the treatment group within the population summarized. Wherever applicable missing data will be summarized as a category.

F-SA-06-01, Version 5.0/30 Dec 2021, SOPs Link: SOP-SA-06

Sponsor: Cellavita Pesquisa Científica Ltda.

Protocol: ADORE-DH

All summary statistics will be displayed to 1 decimal place unless the data recorded is only at the decimal level in which case summary statistics will display data at one additional decimal place. Summary statistics such as minimum or maximum will be displayed as an integer or to the accuracy of data collected if it is only at the decimal level.

The p-value will be displayed up to 4 decimal places. If the p-value is less than 0.0001, it will be presented as' <.0001'; if the p-value is greater than 0.9999, it will be presented as '>.9999'.

Baseline will be defined as the last non-missing measurement before a participant received first treatment of study drug (At baseline visit of V0).

All descriptive statistical summaries and statistical inferences will be performed based on nominal visits (visits at which data are collected).

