#### 7.5.2. Adverse Events

Analysis of Adverse Events will be performed based on the safety population. All Adverse events will be coded using MedDRA ver. 24.1 Sept 2021

Statistical summaries will be performed on general incidence rate of treatment emergent adverse event (TEAEs) including number of events and number of participants with the events. In summarizing the number of participants with adverse events, if a participant has more than one event within the SOC (or PT) they will only be counted once in that row.

The terms Treatment Emergent Adverse Events (TEAEs) and Adverse Events (AEs) are used interchangeably below and unless otherwise specified refer to TEAEs.

Adverse Events will be summarized in the following Tables:

- Overall one page summary of TEAEs.
- Summary of TEAE's by SOC & PT sorted by total number of participants with the TEAE within a SOC and within SOC by total number of participants within a PT. This sort order will also be used in other Tables by SOC and PT indicated below.
- Summary of Severe TEAE's by SOC & PT.

- Summary of TEAE's by SOC, PT and Maximum Severity within SOC or PT. The order for displaying severity will be: Mild, Moderate, Severe.

- Summary of TEAE's Related to Study Drug by SOC PT. For this Table any AE's classified as Certain, Probable/Likely, Possible will be included.
- Summary of TEAE's by SOC, PT and Maximum Relationship to Study Drug within SOC or PT. The order for displaying Relationship to Study Drug will be: Conditional/Unclassified, Unlikely, Possible, Probable/Likely, Certain,.

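### The adverse event tables pool all nine infusions, and the vital-sign section defines no change from the same-visit pre-infusion reading, the first infusion included

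*SAP*

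**What the plan says.** **Exposure.** Protocol 6.3: "Each participant will receive three cycles of three consecutive administrations (one every 30 days) with the drug according to randomization". That makes nine infusions, the same count as SAP 6 uses: "A Per Protocol (PP) population will be defined as all participants who received all 9 infusions".

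**Adverse events.** SAP 4.2.2 counts as a TEAE any event starting at or after the first administration. SAP 7.5.2 plans an overall summary, a table by system organ class (SOC) and preferred term (PT), and tables of severe events, maximum severity, related events and maximum relationship. Numbers of events and of participants are both reported, and for participant counts "if a participant has more than one event within the SOC (or PT) they will only be counted once in that row". No table is split by cycle, infusion number or time since infusion. On timing, Protocol 8.7.1.1.3 says "The safety assessment will be performed at the end of each cycle", verified through AE incidence and causality. SAP 7.6 states that the SAP replaces the protocol's analysis.

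**Vital signs.** SAP 7.5.5: "Vital signs data will be summarized by change and % change from Baseline to each post baseline scheduled visit". The reference value is set in SAP 7.1: "Baseline will be defined as the last non-missing measurement before a participant received first treatment of study drug (At baseline visit of V0"). The next sentence of 7.5.5 says that at dosing visits readings were taken before, during and after administration and will be summarized in that form. A third element compares abnormalities at baseline with those at the worst post-baseline visit.

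**Named risks.** Protocol 9.5 cites a meta-analysis in which "there is a significant correlation between cell therapy and the onset of transient fever". Its Table 05 of theoretical risks includes infusion toxicity, rejection of the administered cells and "Unwanted immune response".

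**The concern.** An allogeneic product given nine times over about 300 days raises two separate safety questions: what happens around an infusion, and whether that changes with repeated exposure. The second bears directly on the immune risk that the protocol names. SAP 4.3 marks anti-drug antibodies as not applicable, so clinical events and vital signs by exposure number are among the main signals available.

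The AE summary tables cannot answer the second question, because opposite time patterns can produce the same totals. The stated vital-sign change is a poor measure for the first. At the ninth infusion it sets a reading taken during the infusion against a value about 300 days old, so an acute effect is mixed with disease progression and visit-to-visit variation. At the first infusion, V0 is itself the baseline visit, so a literal reading gives no change at all.

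**Working it through.** **Counts from the documents**

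- Infusions per participant: 3 cycles × 3 administrations = 9, matching dosing visits V0, V1, V2, V4, V5, V6, V8, V9 and V10. This reproduces the SAP's figure.
- Participants: 14 + 14 + 7 = 35, of whom 28 are on active treatment.
- Planned infusions: 35 × 9 = 315 (28 × 9 = 252 active, 7 × 9 = 63 placebo). V0 holds 35 of them, which are all the first exposures.

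**Can the AE summary tables separate different time patterns?**

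The documents give no reaction risk per infusion, so the risks p_i below are assumptions, with independence between infusions.

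Proportion ever affected = 1 − Π(1 − p_i). Expected events per participant = Σp_i.

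- Flat 15%: 1 − 0.85^9 = 0.768; events 9 × 0.15 = 1.35.
- Rising 3%, 6%, …, 27%: 1 − (0.97 × 0.94 × … × 0.73) = 1 − 0.223 = 0.777; events 0.03 × 45 = 1.35.

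Both the participant count and the event count are practically the same, although the second pattern has a ninefold rise. By cycle, in 28 active participants, they separate:

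| Pattern | Cycle 1 | Cycle 2 | Cycle 3 |
|---|---|---|---|
| Flat 15% | 28 × 0.45 = 12.6 | 12.6 | 12.6 |
| Rising 3% to 27% | 28 × 0.18 = 5.0 | 28 × 0.45 = 12.6 | 28 × 0.72 = 20.2 |

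At lower assumed risks the result is the same. In 28 active participants a flat 5%, a rise from 1% to 9% and a fall from 9% to 1% each give 12.6 expected events in total, with 10.35, 10.41 and 10.41 participants affected. By cycle the expected events are 4.2/4.2/4.2, 1.68/4.2/6.72 and 6.72/4.2/1.68.

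**What does the choice of reference cost for vital signs?**

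Let a reading vary between visits with SD b and within a session with SD w, all deviations independent. Both SDs are assumptions.

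- SD of change from V0 to a later visit: √(2b² + 2w²).
- SD of change from the same-visit pre-infusion reading: √2 × w.

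| b, w (mmHg) | From V0 | Same visit | Ratio |
|---|---|---|---|
| 8, 5 | √178 = 13.3 | 7.1 | 1.9 |
| 5, 6 | √122 = 11.0 | 8.5 | 1.3 |
| 12, 3 | √306 = 17.5 | 4.2 | 4.1 |

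The direction does not depend on the values: for any b above zero, the same-visit reference is less variable.

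**Where do the V0 readings go?**

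Baseline is the last value before the first infusion, taken at V0. The change table runs to post-baseline scheduled visits, and the abnormality summary takes the worst post-baseline visit. If post-baseline means a visit after V0, the V0 during and after readings enter neither. If it means any reading after the baseline measurement, they could enter both. The SAP does not say which.

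**The case against.** A reader might infer that the SAP does not tie safety data to the infusions at all, that first-infusion reactions are lost, or that a growing reaction could not be seen anywhere. The documents do not support any of these.

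- The sentence after the quoted one in SAP 7.5.5 commits to before, during and after summaries at dosing visits. V0 is a dosing visit. SAP 7.1 bases descriptive summaries on nominal visits, and each dosing visit is one infusion, so this comes close to a display by infusion number.
- Adverse events at the first infusion count as TEAEs and enter the AE tables.
- Event counts are planned as well as participant counts. The once-only rule applies to participants within a row.
- Laboratory changes are shown by scheduled visit, with samples after each cycle at V3, V7 and V11. Physical abnormalities are shown at each visit. All eCRF data are listed, so with 35 participants event timing can be read from the listings.

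Protocol 8.7.1.1.3 can also be read as fixing when safety is assessed rather than promising AE tables by cycle. Protocol 9.5 calls the Table 05 risks theoretical, and the meta-analysis it cites found no significant association with acute infusion toxicity. Finally, the proposed cells are small: at an assumed 5% risk, one infusion yields 14 × 0.05 = 0.7, 0.7 and 7 × 0.05 = 0.35 expected participants per arm.

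All of this stands, and it confines the point to two gaps. The AE summary tables carry no timing, and listings are not a prespecified summary. The before, during and after display does not say whether a change within the visit will be shown. Small cells are a reason to keep the tables descriptive, which fits SAP 5, where no safety testing is planned.

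**Conclusion.** The point holds in two limited parts.

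First, every TEAE table in SAP 7.5.2 pools nine infusions, and the protocol's end-of-cycle assessment has no AE counterpart by cycle in the SAP. The AE summary tables therefore cannot distinguish rising, flat and falling reaction rates (76.8% against 77.7% ever affected, 1.35 events per participant in both, under assumed risks). Whether the protocol meant tables by cycle is open; that the SAP has none is not.

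Second, SAP 7.5.5 under-specifies acute vital-sign change. The readings will be summarized, but the only change defined uses the V0 pre-dose value, and the status of the V0 during and after readings is unclear. Under assumed SDs, the V0 reference is 1.3 to 4.1 times as variable as a same-visit reference.

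The risks and SDs are illustrative and do not come from the documents. The efficacy analysis is untouched, and nothing suggests that safety data go uncollected. This is a cheap change worth making, not a flaw that undermines the trial.

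**What to change.** **SAP 7.5.2.** Add descriptive TEAE tables:

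- by cycle of onset: V0 to before V4, V4 to before V8, and V8 to V11. Nominally these windows last 120, 120 and 330 − 240 = 90 days, so show the exposure time beside the counts;
- by infusion number, for events starting on the day of or the day after an infusion, with the participants who received that infusion as denominator. Protocol 7.5 keeps participants in the study after a missed administration, so this denominator can change from one infusion to the next.

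**SAP 7.5.5.**

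- At each dosing visit (V0–V2, V4–V6, V8–V10), define acute change as the during and after readings minus the same-visit pre-infusion reading, tabulated by infusion number.
- Keep change from V0 for pre-infusion and follow-up readings.
- State that V0 during and after readings count as post-baseline for the worst-abnormality summary.

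**Cost.** SAP wording and a few more tables, with no new data. SAP 7.2.1 says the eCRF did not allow partial AE dates, SAP 4.10 records infusion start and stop times, and the vital-sign readings were taken. The drawback is small cells (14, 14 and 7 per arm at most), so the tables are descriptive only and should be labelled so.
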